Name of Finished Product: Tinostamustine hydrochloride (Formerly EDO-S101)		Name of Active Ingredient: Tinostamustine hydrochloride
Protocol No.: EDO-S101-1004	Temporary (T) No.:	<EUDRACT><IND> No.: CCI [REDACTED]
Drug Concentration Measurements: Serial blood samples for PK analysis will be collected before, duration, and after tinostamustine administration according to the schedule in Table 1 . Samples will be collected, labelled, stored and shipped as detailed in the Laboratory Manual.		
Bioanalytical Methods: A fully validated LC-MS/MS method for the determination of EDO-S101 and its metabolites (M2 and M8) in human plasma will be utilised. CCI [REDACTED] [REDACTED]		
Safety Assessments: Safety will be assessed by documentation of AEs, safety laboratory tests (hematology and clinical chemistries), ECOG performance status, vital signs, physical examinations, electrocardiograms (ECGs), and Holter monitoring.  During in-patient hospitalization, patients will be assessed daily for hematologic engraftment until and including the day the patient has an ANC $>0.5 \times 10^9/L$ and platelet count $> 20 \times 10^9/L$ without transfusion support.  To assess for early renal toxicity, creatinine, urea, and uric acid will be assessed on a daily basis from the start of tinostamustine treatment through Day 3 post-ASCT. In case of clinically significant renal toxicity, creatinine, urea, and uric acid will be assessed as long as clinically indicated.		
Statistical Methods:		
Analysis Populations All patients who receive tinostamustine will be included in the safety set.  All patients in the safety set who had at least one post-ASCT response evaluation will be included in the full analysis set (FAS).  All patients in the FAS with no major protocol deviations will be included in the per-protocol (PP) set.		

Name of Sponsor Mundipharma-EDO GmbH		
Name of Finished Product: Tinostamustine hydrochloride (Formerly EDO-S101)		Name of Active Ingredient: Tinostamustine hydrochloride
Protocol No.: EDO-S101-1004	Temporary (T) No.:	<EUDRACT><IND> No.: CCI [REDACTED]

All patients in the safety set with at least one quantifiable pre-dose and one quantifiable post-dose PK plasma concentration will be included in the PK set.
 
Dependent of the specific analysis, these sets will be taken from the cohort for Phase 1, for Phase 2 (RP2D), or both phases pooled.
		

Efficacy Analyses:
 
Summaries for continuous and ordinal variables will include the number of observations (n), arithmetic mean, standard deviation (SD), median, minimum, and maximum. Summaries for categorical variables will include frequency counts and percentages.
 
Superiority testing will be performed on FAS in Phase 2 cohort to investigate the null hypothesis that the primary endpoint of responder rate is below or equal to the gold standard against the alternative hypothesis that it is higher than the gold standard. The gold standard is assumed to be 77.5% (CIBMTR report, December 2017) and a 1-sided, 2-step chi-square test will be performed at the 2.5% level of significance for FAS.
 
For the primary endpoint, also an upper 1-sided 97.5% confidence interval will be calculated for FAS in addition to summary statistics.
 
For the primary endpoint in other sets and for the secondary endpoints of other responder rates in the FAS, also 2-sided 95% confidence intervals will be calculated in addition to summary statistics.
		

Interim Analyses:
 
In Phase 2 of the study, at the completion of the Stage 1 with 31 patients, an interim analysis will be performed using the FAS for the Phase 2 cohort to determine whether enrollment will continue in Stage 2. If >25 of 31 patients in Stage 1 experience a response to treatment, then enrollment will continue into Stage 2, with up to 40 patients planned to be enrolled. However, if ≤25 patients in Stage 1 experience a response to treatment, no further patients will be enrolled (in the ongoing Stage 2 recruitment).
		

Pharmacokinetic Analyses:
 
PK analysis for tinostamustine and its metabolites will be performed using the PK set.
 
PK parameters at all doses will include maximum plasma concentration (<math>C_{max}</math>), time to maximum plasma concentration (<math>t_{max}</math>), half-life (<math>t_{1/2}</math>) area under the plasma concentration curve from 0 to 12 hours (<math>AUC_{0-12}</math>), area under the plasma concentration curve from time 0 to time t (<math>AUC_{0-t}</math>), apparent total clearance (CL/F),
		

Name of Sponsor Mundipharma-EDO GmbH		
Name of Finished Product: Tinostamustine hydrochloride (Formerly EDO-S101)		Name of Active Ingredient: Tinostamustine hydrochloride
Protocol No.: EDO-S101-1004	Temporary (T) No.:	<EUDRACT><IND> No.: CCI [REDACTED]

apparent volume of distribution (Vd/F), and terminal disposition rate constant (<math>\lambda_z</math>). The initial calculation of PK parameters will be performed using non-compartmental analysis. Plasma concentrations and PK parameters will be summarized by dose.
 
Summaries will include the number of observations (n), arithmetic or geometric mean, SD or coefficient of variation (CoV), median, minimum, and maximum.
		

Safety Analyses:
 
Safety data, including changes from baseline if applicable will be summarized at each dose level for the safety set.
 
Summaries for continuous and ordinal variables will include the number of observations (n), arithmetic mean, SD, median, minimum, and maximum. Summaries for categorical variables will include frequency counts and percentages.
		

Sample Size Rationale
 
Across both Phases 1 and 2 of the study, a total of up to ~86 patients may be enrolled.
 
For Phase 1, a formal sample size determination/power calculation was not performed. Based on experience from previously published similar studies, a total number of 9 (minimum) to 12 (maximum) patients in the dose escalation stage of the study are foreseen.
 
For Phase 2 of the study, superiority testing will be performed to investigate the null hypothesis that the primary endpoint of responder rate is below or equal to the gold standard against the alternative hypothesis that it is higher than the gold standard. The gold standard is assumed to be 77.5% (CIBMTR report, December 2017) and a one-sided chi-square test will be performed at the 2.5% level of significance. For power considerations, the alternative working hypothesis is that the responder rate for the study drug is at least 90%.
 
In the methodology proposed by Simon (Simon, 1989), a Phase 2 design can be represented by 4 numbers: N1, R1, N, and R. N1 is the sample size in the first stage. R1 is the critical value in the first stage. If R1 or fewer responses occur in the N1 patients, the study treatment is rejected. N is the combined sample size for both the first and second stages. R is the critical value in the combined sample. If R or fewer of the N patients respond, the study treatment is rejected at the end.
 
The design is found with PASS Sample Size Software through an exhaustive search of all possible designs (combinations of R1, N1, R and N) that control alpha (0.025) and beta (0.20, meaning power is
		

Name of Sponsor Mundipharma-EDO GmbH		
Name of Finished Product: Tinostamustine hydrochloride (Formerly EDO-S101)		Name of Active Ingredient: Tinostamustine hydrochloride
Protocol No.: EDO-S101-1004	Temporary (T) No.:	<EUDRACT><IND> No.: CCI [REDACTED]
0.80). With the minimax approach, the design is selected that has the lowest N. Per the minimax design, 31 patients are to be enrolled in Stage 1. If $>25$ of 31 patients (in the FAS) in Stage 1 experience a response to treatment, then enrollment will continue in Stage 2, with up to 40 patients planned to be enrolled. However, if $\leq 25$ patients in Stage 1 experience a response to treatment, no further patients will be enrolled. Thus, a total of up to 71 patients will be enrolled in Phase 2. If the total number of patients who experience a response is $\geq 62$ of 71, then the study is considered a success.		
Schedule of Events The schedule of events is presented in Table 1 .		

**Table 1: Schedule of Events (Phases 1 and 2)**

Procedure	Screening	Conditioning	ASCT	Post-ASCT Follow-up 			
	D-28 to -1	D-1	D0	M1	M2	D100 (±7 days)	D130 (±7 days)
Written informed consent 	X						
Eligibility review	X		X				
Demographics	X						
Medical history	X						
HCT-CI	X						
Cancer history, including history of prior ASCT and other treatments	X						
ECHO or MUGA scan	X						
Pulmonary function testing 	X						
Infectious disease screening 	X						
Pregnancy test 	X						
ECOG performance status	X		X	X	X	X	
Complete physical examination	X						
Targeted physical examination		X	X	X	X	X	
Height	X						
Weight	X		X	X	X	X	
Vital signs 	X	X	X 	X	X	X	
Continuous Holter monitoring		X 					
12-lead ECG 	X 	X 		X			
Hematology 	X	Repeat daily until hospital discharge					
Kidney function tests (creatinine, urea, and uric acid)		Daily from the start of tinostamustine through Day 3 post-ASCT					

*CONFIDENTIAL*

Procedure	Screening	Conditioning	ASCT	Post-ASCT Follow-up 			
	D-28 to -1	D-1	D0	M1	M2	D100 (±7 days)	D130 (±7 days)
Clinical chemistries 	X	X	X	X	X	X	
Coagulation parameters: PT and/or INR, aPTT	X		X	X		X	
Urinalysis 	X						
Tinostamustine administration 		X					
PK sample collection		X 					
ASCT 			X				
Disease assessments							
Skeletal survey 	X						
Bone marrow aspirate and biopsy 	X					D100 (±7 days) 	
Serum / urine M protein quantitation	X			X	X	X	X
Immunoglobulin quantitation (IgA, IgG, and IgM [required]; IgD, IgE [optional])	X			X	X	X	X
Free light chain analysis	X			X	X	X	X
Disease response assessment 	X			X	X	X	
Evaluation for MRD-N						D100 (±7 days) 	
AE monitoring 	AEs, including SAEs, are to be documented from the provision of written informed consent through Day 100.						
Prior/concomitant medications 	All medications administered within 28 days before Day 1 through Day 100 are to be documented.						

1. Patients will be evaluated daily on an inpatient basis until engraftment criteria are met and the patient is discharged from the hospital. Thereafter, study center visits will be performed on an outpatient basis. Visit M1: D30 (±5days); visit M2: D60 (±5days)
2. Written informed consent is to be obtained before the performance of any study-related procedures.
3. Pulmonary function testing is to include FEV1, FVC, and DLCO.
4. Infectious disease marker testing is to include, at a minimum, human immunodeficiency virus (HIV) types 1 and 2, hepatitis B virus (HBV) panel (HBV surface antigen, HBV surface antibody, HBV core antibody, HBV e-antigen), hepatitis C virus (HCV), Treponema pallidum, CMV, and Epstein-Barr virus.
5. Urine or serum pregnancy testing will be performed for women of childbearing potential. Pregnancy testing is to be repeated on study any time pregnancy is suspected.
6. Vital signs include blood pressure, pulse, respiratory rate, and temperature. Vital signs are to be measured after patient is sitting for 3-5 minutes.

7. Perform assessment both pre- and post-treatment.
8. ECGs (12-lead) are to be performed after the patient is supine for 5 minutes. Repeat ECGs as clinically indicated. Screening ECGs will be reviewed centrally. Regarding other 12 lead ECGs: the investigator or the sponsor may request expedited central review of ECGs, as clinically indicated.
9. Continuous Holter monitoring will be performed on Day -1, the day of tinostamustine administration. Holter monitoring will commence 15 minutes prior to the start of the infusion on Day -1 and will continue through 24 hours following the end of infusion. Patients should be resting comfortably in the supine or semisupine position for 15 minutes prior to each of the following timepoints: 0 [before start of infusion] then after start of the infusion at 15, 30, 45, and 60 minutes and 3, 6, and 24 hours following the start of the infusion. At time 0 and at all time points after infusion, ECGs readings will be extracted in triplicate, with each ECG separated by 5 minutes ( $\pm 2$  minutes), for establishment of baseline for the purposes of cardiac safety analyses. The Holter monitor flashcards will be sent to eResearch Technology, Inc., for processing.
10. The Investigator's interpretation of ECGs is to be used for patient management during the study; the central reader interpretation of ECGs extracted from Holter monitoring will be used to determine all ECG data for study endpoints including baseline QTcF interval for cardiac safety analyses and DLTs.
11. A triplicate ECG will be performed during Screening to determine patient eligibility for the study. Furthermore, on Day -1, a triplicate ECG is to be performed before study drug administration and a single ECGs will be performed at 30 and 60 minutes after the start of study drug administration for assessment by the site. Another single ECG will be performed at visit on day 30 ( $\pm 5$  days). ECGs are to be repeated by the Investigator, as clinically indicated.
12. Hematology parameters minimally include WBC count and differential (lymphocytes, monocytes, basophils, eosinophils, neutrophils), red blood cell (RBC) count, hematocrit, hemoglobin, and platelet count.
13. Serum chemistry parameters minimally include alanine aminotransferase (ALT), albumin, alkaline phosphatase (ALP), aspartate aminotransferase, (AST), bicarbonate, bilirubin (total, direct, and indirect), calcium, magnesium, chloride, glucose, lactate dehydrogenase (LDH), phosphate, potassium, sodium, and total protein.
14. Urinalysis includes appearance, color, pH, specific gravity, ketones, leukocytes, protein, glucose, bilirubin, urobilinogen, and occult blood.
15. The tinostamustine dose will be administered one day before ASCT (Day -1), at least 24 hours pre-ASCT.
16. Blood samples for PK are to be collected immediately pre-infusion of tinostamustine and 30, 45, and 60 ( $\pm 5$ ) minutes and then at 3, 6, and 24 hours ( $\pm 15$  minutes) and then 48 hours ( $\pm 30$  minutes) after the start of infusion. Blood samples for PK assessment should be collected following the 15-minute supine resting periods described for the continuous Holter recordings. PK samples are to be collected from the arm opposite of that used for tinostamustine administration.
17. On Day 1, ASCs will be administered IV according to standard institutional practice. If the CD34+ product is of large volume, the infusion can be given over 2 days.
18. A skeletal survey (plain radiographs, or any other method used as standard care at the site, of the skull, spine, ribs, pelvis, humeri and femora) will be performed at Screening if not performed within the previous 3 months. Thereafter, skeletal survey and/or other imaging studies are to be performed as clinically indicated.
19. Bone marrow aspirate and trephine biopsy are to be performed during Screening. Bone marrow aspirate and biopsy are to be repeated during treatment as clinically indicated, at the Investigator's discretion, and at any time CR is suspected.
20. Any patient who achieves a CR will have peripheral blood and bone marrow collected at Day 100 ( $\pm 7$  days) for assessment of evidence of MRD-N via next-generation flow cytometry.
21. Disease response will be assessed by the Investigator using the IMWG Criteria. Confirmation should be obtained for biochemical markers but is not necessary for bone marrow or imaging studies. There is no specific time interval required between the 2 evaluations, the confirmatory tests ideally should be performed approximately 4 weeks after the initial evaluation.
22. AEs will be documented as occurring pre-conditioning (i.e., pre-tinostamustine); during conditioning (i.e., after the start of the first tinostamustine infusion through immediately before the start of autologous stem cell [ASC] infusion); or after ASCT (i.e., after the start of ASC infusion).
23. Concomitant medications will be documented as administered pre-conditioning (i.e., pre-tinostamustine); during conditioning (i.e., after the start of the first tinostamustine infusion through immediately before the start of ASC infusion); or after ASCT (i.e., after the start of ASC infusion).

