## **6. STUDY CONDUCT**

### **6.1. Patient Identification and Enrollment**

To ensure accurate and timely monitoring of patient enrollment, the following procedures will be implemented:

- Patients who are candidates for enrollment into the study will be assigned a sequential and unique patient number by the Investigator after the patient has provided written informed consent. Once a patient number has been assigned, it cannot be reused.
- Patients who have provided written informed consent will be evaluated for eligibility by the Investigator to ensure that the entry criteria (see [Section 5.1](#) and [Section 5.2](#)) have been satisfied and that the patient is eligible for participation in this clinical study. An eligibility form will be provided by the Sponsor, or designee for this evaluation.
- The Investigator or the Investigator's research staff will provide eligibility information to the Sponsor or designee. After confirmation, the Sponsor or designee will provide the Investigator with written verification of each patient's enrollment.
- No patient may be enrolled prior to confirmation of a patient's eligibility by the Sponsor or designee.
- Patients who are enrolled but not treated with tinostamustine followed by ASCT will be replaced.
- Investigators will be notified by the Sponsor or designee when enrollment in a given dose cohort / study part is closed and enrollment into the next dose cohort / study part can begin. (Investigators will be consulted in all dose escalation decisions.)
- Investigators will be notified by the Sponsor or designee if the study is placed on administrative hold, when it is completed, or is closed to further patient enrollment.

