### **6.2. Patient Management**

All patients must provide written informed consent before any samples are collected or evaluations performed in this study that are not part of standard patient care. Patients will be evaluated for study eligibility during the Screening period, within 28 days before baseline (Day 1; the Day of ASCT).

Patients who are determined to be eligible, based on Screening assessments, will return to the clinic to receive the tinostamustine conditioning regimen; the tinostamustine dose will be administered 24 hours pre-ASCT (on Day -1).

On Day 1, ASCs will be administered IV according to standard institutional practice.

During in-patient hospitalization, patients will be assessed daily for toxicity through Month 1 Day 30 ( $\pm 5$  days) post-ASCT or until all transplant-related toxicity resolves. Patients will be discharged from the study center once engraftment criteria are met (see [Section 8.3](#)).

Thereafter, patients are to be followed at Month 2 Day 60 ( $\pm 5$  days) and Day 100 ( $\pm 7$  days).

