### **6.4. Treatment Discontinuation Criteria**

Once tinostamustine has been infused it will be medically negligent to stop transplant and supportive therapy for the particular patient. In the event of consent withdrawal during or following conditioning or the development of complications that, in the Investigator's opinion, puts the patient at risk with continued protocol-specified treatment, the Medical Monitor should be contacted immediately to discuss management of the patient.

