### **6.5. Study Discontinuation Criteria**

Patients will be informed that they have the right to withdraw from the study at any time for any reason, without prejudice to their medical care. The Investigator also has the right to withdraw patients from the study for any of the following reasons:

- Patient non-adherence to protocol requirements.
- Patient unwillingness to continue in the study.
- Any other reason, based upon the medical judgment of the Investigator.

The reason for study withdrawal is to be documented in the patient's source documents and electronic case report form (eCRF).

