**Item 2: Day of Autologous Stem Cell Transplant (ASCT)**

Currently, Protocol Clarification memo dated 21Sep18 and Protocol Version 2.0 18 June 2018 in all places except the header of the Schedule of Events on pages 17 and 18, that ASCT is on Day 1.

As is standard practice, it should say that the day of ASCT is study Day 0.

This clarification does not impact patient safety. Please submit this clarification to your IRB/IEC for their review, if required. In addition, file this letter and any IRB/IEC correspondence in your study files.

This clarification will be incorporated into a subsequent protocol amendment should one be required.

I am available to discuss any questions or comments you may have.

PPD  
Sincerely,  
PPD

PPD            MD    PP  
D  
Mundipharma-EDO GmbH

Cc: EDO-S101-1004 Study Team  
Cc: EDO-S101-1004 Trial Master File

**Date:** 14 December 2018

**To:** EDO-S101-1004 (TITANIUM 1) Investigator and Site Staff

**Protocol Title:** A Phase 1/2 Open-Label Trial of Tinostamustine Conditioning and Autologous Stem Cell Transplantation for Salvage Treatment in Relapsed/Refractory Multiple Myeloma (TITANIUM 1)

**Protocol Version:** 2.0, 18 June 2018

**Subject:** Protocol Clarification Memo

---

Dear Investigator and Site Staff,

Please see below clarifications for EDO-S101-1004 version 2.0 protocol 18 June 2018. An amendment is forthcoming with these changes incorporated.

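### The only repeat eligibility review is scheduled on the ASCT day, after the Day -1 tinostamustine dose, so it cannot prevent dosing of a patient who has lost eligibility since Screening

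*Protocol*

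**What the plan says.** The "Eligibility review" row of Table 1 has two marks, one under Screening (D-28 to -1) and one under ASCT (D0). The Conditioning column (D-1) is empty. Protocol versions 1.0 and 2.0 agree on this.

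Footnote 15 to Table 1 fixes the dose: "The tinostamustine dose will be administered one day before ASCT (Day -1), at least 24 hours pre-ASCT". The clarification memos changed the label of the ASCT day and then changed it back. The October 2018 memo settles that "it should say that the day of ASCT is study Day 0". No memo moves the eligibility mark.

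Section 6.1 requires the sponsor or its designee to confirm eligibility before enrollment. Section 6.2 then states: "Patients who are determined to be eligible, based on Screening assessments, will return to the clinic to receive the tinostamustine conditioning regimen". It describes no further check on the day of dosing.

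Section 6.4 covers the period after dosing: "Once tinostamustine has been infused it will be medically negligent to stop transplant and supportive therapy for the particular patient". Its next sentence sends consent withdrawal, and complications that make continued treatment risky, to the Medical Monitor. It does not mention a patient found to be ineligible.

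**The concern.** A second eligibility review has a purpose only if it can change what happens next. Here the step that cannot be undone is the conditioning infusion, and the review is scheduled after it. If a patient has developed an infection or an abnormal potassium since Screening, the scheduled review finds this once the drug has been given. Withholding the cells is then described as negligent. Stopping in time would depend on someone noticing, without a scheduled prompt, before the infusion begins.

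What is at stake is patient safety. The December 2018 memo (Item 10) lists infection and QTc prolongation among the possible risks of tinostamustine. It adds that high-dose conditioning causes myelosuppression and raises the risk of infection. A patient who starts conditioning with an uncontrolled infection is one whom exclusion 3 is meant to keep out.

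**Working it through.** No sample-size or error-rate figure bears on this point. The check is the order of events, one interval, and a sorting of the criteria.

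1. **Column alignment.** The tinostamustine row of Table 1 has its only mark under D-1, and the ASCT row has its only mark under D0. Read against these, the eligibility row has marks at Screening and D0 and none at D-1.

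2. **Order of events.** Screening review (D-28 to -1), then tinostamustine (D-1), then ASCT and repeat review (D0). The repeat review always follows the dose. If ASCT is called Day 1, as in the body of version 2.0, the order is the same.

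3. **Interval from Screening review to dose.** The longest gap is 28 − 1 = 27 days (review on D-28, dose on D-1). The shortest is 1 − 1 = 0 days (both on D-1). The 27 days is a maximum, not a typical value.

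4. **Which criteria are exposed.**
   - Inclusions 7 to 10 (creatinine clearance, LVEF, pulmonary function, liver function) expressly accept results from up to 28 days before ASCT, so they are outside this point.
   - Exclusion 10 (washouts) and exclusion 11 (QT-prolonging drugs) can be planned or restricted ahead. Exclusion 10 counts the investigational-agent washout back from the expected start of treatment. Section 7.8.1 prohibits anti-myeloma and QT-prolonging drugs during participation, and the January 2019 memo restricts antiemetics around the dose. No scheduled pre-dose check confirms compliance.
   - Exclusion 3 (uncontrolled acute infection) and inclusion 11 (potassium in the local normal range) carry no such time allowance and can change within days. Inclusion 11 does permit supplementation, so a low value may be correctable.

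   These last two are the chief exposed criteria. The list is not meant to be exhaustive.

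5. **What Day -1 already contains.** Table 1 schedules clinical chemistries (potassium is named in footnote 13), vital signs (temperature, footnote 6), a targeted examination and a triplicate ECG. Of these four, only the ECG is stated to precede the dose (footnote 11). That footnote gives the Screening ECG an eligibility purpose and the Day -1 ECGs the purpose of site assessment. None of the four carries an eligibility decision.

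**The case against.** The strongest reply is that dosing is already well guarded. The Screening review may be done as late as Day -1. Sponsor confirmation follows it under section 6.1, and SAP section III.D counts a patient as enrolled only once all criteria are confirmed in the eCRF. The date of that last confirmation is not stated, so the gap from it to the dose is unknown and may be well under 27 days. The December 2018 memo has ECGs read at the site before the infusion. Adverse events are recorded from consent onward. Section 6.5 lets the investigator withdraw a patient for "Any other reason, based upon the medical judgment of the Investigator", and section 6.1 foresees the case: "Patients who are enrolled but not treated with tinostamustine followed by ASCT will be replaced". An investigator who sees a fever on Day -1 would be expected to hold the infusion.

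Most of this stands, and it limits the point. These controls either come before enrollment and are not repeated, or depend on unscheduled judgment. The December memo's infection statement describes what conditioning does afterwards, and its daily evaluation is not tied to a decision to dose. It shows why infection matters here, not that infection arises between Screening and Day -1.

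The blank at D-1 may also be a drafting slip. The Weight row has the same pattern (Screening and D0, none at D-1), although section 9.2.2 bases the dose on a weight documented before tinostamustine starts on Day -1. That is plausible but unproven. The correction is the same either way.

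**Conclusion.** The point holds in a limited form. The only scheduled repeat eligibility review comes after the irreversible step and cannot prevent the dose. No scheduled point before the infusion re-checks criteria that can change quickly, over a gap of 0 to 27 days from the Screening review. This rests on reading Table 1 as printed and on the memos leaving the row alone.

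A reader might infer more than the documents support:

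- **That the review falls at least 24 hours after the dose.** Footnote 15 sets the interval from dose to ASCT. A D0 review done before the cells are infused could be somewhat sooner. Only its position after the dose is established.
- **That section 6.4 absolutely bars stopping the transplant.** It calls stopping negligent but refers at-risk patients to the Medical Monitor, so a D0 finding could still prompt that contact.
- **That nothing guards the dose, or that ineligible patients were dosed.** Several controls precede it, and the documents report no such case.
- **That this gap contributed to the discontinuation.** SAP section I.C cites safety signals and does not link them to eligibility checking.

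No endpoint, decision rule or error rate is affected. Because the study was discontinued, the change matters for a restart or for another protocol that reuses this schedule.

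**What to change.** Move the second eligibility mark in Table 1 from D0 to D-1, to be completed before the infusion. Add a footnote requiring these checks before dosing:

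- potassium, sampled and resulted before the dose, with supplementation or delay if out of range;
- signs of infection, from temperature and the targeted examination;
- concomitant QT-prolonging drugs;
- compliance with the exclusion 10 washouts.

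Add a D-1 mark to the Weight row, so that the table shows the dosing weight that section 9.2.2 calls for.

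The cost is two table marks and one footnote. No new visit or test is needed: the assessments are already scheduled on Day -1, and section 7.8 already requires timed medication records on PK sampling days, which include Day -1. The real downside is operational. Day -1 chemistries must be drawn and resulted before the infusion, which may delay some doses. The formal review on D0 is given up, but it comes too late to affect dosing.
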